16.0 QUALITY CONTROL AND QUALITY ASSURANCE

Written SOPs will be followed to ensure that the study is conducted and data are generated, documented (recorded), and reported in compliance with the protocol, GCP, and the applicable regulatory requirements. Quality control will be applied to each stage of data handling. Regular monitoring, as defined in ICH GCP, Section 1.8, “The act of overseeing the progress of a clinical trial, and of ensuring that it is conducted, recorded, and reported in accordance with the protocol, SOPs, GCP, and the applicable regulatory requirement(s)”, will be conducted throughout the conduct of the study.

The purpose of monitoring is to verify that:

- Rights and well-being of the human subjects are protected
- The reported study data are accurate, complete, and verifiable from source documents
- The conduct of the study is in compliance with the currently approved protocol/amendment(s), with GCP, and with the applicable regulatory requirements
- Monitoring is an integral role in the quality control of a clinical trial and is designed to verify the quality of the study

To fulfill the Quality Assurance requirements of GCP, audits will be conducted to assess and assure the reliability and integrity of a study’s quality control systems and recognized standards.

The purpose of an audit is to:

- Ensure participant safety
- Assure compliance to study protocol procedures, regulatory requirements, and SOPs
- Assure data quality

CONFIDENTIAL

Verrica Pharmaceuticals Inc.

VP-102 (Cantharidin)

Clinical Protocol

VP-102-104

17.0 FINANCING AND INSURANCE

The financing and insurance for this study are outlined in the Clinical Trial Agreement.

18.0 PUBLICATION POLICY

The data generated in this clinical study are the exclusive property of the Sponsor and are confidential. Authorship on any publication of the results from this study will be based on contributions to study design, enrollment, data analysis, and interpretation of results.

Appendix 1: Version History and Summary of Changes

SUMMARY OF PROTOCOL CHANGES: VP-102-104

Version history:

DOCUMENT	VERSION	DATE
Protocol VP-102-104	1	09 May 2019
Protocol VP-102-104	2	07 August 2019

SECTIONS/PAGES CHANGED	DESCRIPTION OF CHANGES
Administrative Update Throughout Protocol	Updated Version to 2.0 and updated version date to 07 August 2019.
Title of Study (pg. 1) Protocol Synopsis: Title of Study (pg. 4)	The study title was updated to include “Cantharidin” and the study acronym of CARE-1 was added. CARE stands for C Antharidin R egimen in E xternal Genital Warts.
Protocol Synopsis: Objectives (pg. 4) Section 5: Study Purpose and Objectives (pg. 41)	Added clarification that secondary and exploratory objectives will be applicable to both Part A and Part B of the study.
Protocol Synopsis: Exploratory Objectives (pg. 5) Section 5: Study Purpose and Objectives (pg. 41)	The change from baseline in total wart area and the percent change from baseline in total wart area were added as two new exploratory objectives. Removed reference to “Part B Only” as these will be applicable to both parts of the study.
Protocol Synopsis: Exploratory Efficacy Endpoints (pg. 13) Section 11.1: Efficacy Parameters (pg. 87-88)	The endpoints associated with the two new exploratory objectives evaluating the change from baseline in total wart area and the percent change from baseline in total wart area were added.
Section 8.2.2: Removal of Surgical Tape and Study Drug (pg. 56) Section 9.7.3: Removal of Surgical Tape (pg. 76)	The reference to “warm” water was removed, as it is not required for the water to be warm to remove the study drug.
Section 9.2: Screening Period (pg. 64) Section 9.3.1.1: Day 1 (Treatment Visit 1) (pg. 66)	Blood pressure was inadvertently referenced as part of the vital sign procedure, but instead should have said heart rate. All references to blood pressure have been replaced with heart rate to

CONFIDENTIAL

Verrica Pharmaceuticals Inc.

VP-102 (Cantharidin)

Clinical Protocol

VP-102-104

SECTIONS/PAGES CHANGED	DESCRIPTION OF CHANGES
Administrative Update Throughout Protocol	Updated Version to 2.0 and updated version date to 07 August 2019.

Section 9.3.1.3: In-person Visit at 48 hours (± 8 hours) after Study Drug Administration (Part A only) (pg. 67)
 
Section 9.3.2.1: Day 1 (Treatment Visit 2, Treatment Visit 3, Treatment Visit 4) (pg. 68)
 
Section 9.4: End-of-Treatment Visit: Study Day 84 (-0/+8 days) (pg. 71)
 
Section 9.5: Follow-up Visits on Study Day 112 (± 7 days) and Study Day 147 (± 7 days) (End-of-Study) (pg. 73)
 
Section 9.6: Unscheduled Visit (pg. 74)
	match footnote 'h' in Table 1. Study Schedule of Assessments and Procedures (Part A and Part B)
Section 10.8: Risks for Women of Child-bearing Potential or During Pregnancy (pg. 86)	The definition of pregnancy was clarified to include any genetic contribution to a pregnancy by both male and female subjects.

Synopsis: Exclusion Criteria (pg. 10)
 
Section 7.2: Subject Exclusion Criteria (pg. 50)
	Removed reference to neoplasia in exclusion criteria #8, as it is already covered in exclusion criteria #15.
Section 14.1: Investigator Information (pg. 93)	Corrected reference to Manual of Operations to Investigator Brochure. The reference to a Manual of Operations was an oversight.
Section 14.2: Investigator's Study File (pg. 93)	Removed reference to Manual of Procedures, as there is not a need for this document for this protocol. The reference to a Manual of Procedures was an oversight.
Section 14.8: General Information (pg. 95)	Corrected reference to Manual of Operations to Instructions For Use. The reference to a Manual of Operations was an oversight.

List of Abbreviations

AE	Adverse Event
ATC Class	Anatomical/Therapeutic/Chemical Class
BMI	Body Mass Index
CMH	Cochran-Mantel-Haenszel
COVID-19	Coronavirus 19
CRF	Case Report Form
CSR	Clinical Study Report
EDC	Electronic Data Capture
EGW	External Genital Wart
EOS	End of Study
EOT	End of Treatment
ERT	Evaluation of Response to Treatment
ITT	Intent to Treat
LOCF	Last Observation Carried Forward
LSR	Local Skin Reactions
MCMC	Monte Carlo Markov Chain
MedDRA	Medical Dictionary for Regulatory Activities
MMRM	Mixed-effect Model Repeated Measure
PP	Per Protocol
SAP	Statistical Analysis Plan
TEAE	Treatment Emergent Adverse Event
TFL	Tables, Figures, Listings
WHO	World Health Organization

1. Introduction

The purpose of this document is to ensure the statistical methodologies that will be used are complete and appropriate to allow valid conclusions regarding the study objectives. The study background, design and subject assessments for the study are described in the study specific protocol. Results obtained from the analyses outlined in this document will be the basis of the final clinical study report (CSR) for this protocol. Any deviations from this statistical analysis plan (SAP) will be documented in the final CSR.

2. Study Rationale and Objectives

2.1. Study Rationale

There have been no studies with VP-102 conducted in subjects with genital warts. This is a new indication for VP-102. It is anticipated that subjects in this study who are randomized to VP-102 will experience similar therapeutic benefits as those subjects previously treated with VP-102 or 0.7% w/v cantharidin.

2.2. Study Objectives

2.2.1. Primary Objectives

Part A (Dose Regimen Finding)

The primary objectives for Part A are:

- to evaluate the three regimens of application of VP-102 (2-hour, 6-hour, 24-hour duration of skin exposure) in subjects with external genital warts (EGW) and identify the two best regimens by assessing safety and tolerability of VP-102 when administered topically after all subjects have completed a 48-hour assessment
- to evaluate the efficacy of VP-102 when administered topically to EGW once every 21 days for up to 4 applications by assessing the proportion of subjects achieving complete clearance of all treatable warts (baseline and new) at the Study Day 84 End-of-Treatment (EOT) Visit.

Part B (Safety and Efficacy)

The primary objective for Part B is to evaluate two regimens of application of VP-102 in subjects with EGW and identify the regimen with the best risk:benefit profile when administered topically once every 21 days for up to 4 applications.

2.2.2. Secondary Objectives

The secondary objectives of this study for Part A and B are:

- to assess the safety and tolerability of VP-102 in subjects with EGW by evaluating adverse events (AE) including expected local skin reactions (LSR), vital signs, and concomitant medications.
- to evaluate the efficacy of VP-102 when administered topically to EGW once every 21 days for up to 4 applications by assessing the proportion of subjects achieving complete clearance of all treatable warts (baseline and new) at Treatment Visit 2, 3, 4, and Follow-up Visits on Study Day 112 and 147 End of Study (EOS).
- to evaluate the efficacy of VP-102 by assessing the change from baseline in the number of treatable warts (baseline and new) at each scheduled post baseline visit.
- to evaluate the efficacy of VP-102 by assessing the percent change from baseline in the number of treatable warts (baseline and new) at each scheduled post baseline visit.
- to evaluate the efficacy of VP-102 by assessing the proportion of subjects exhibiting 75% and 90% clearance of all treatable warts (baseline and new) at each scheduled post baseline visit.

2.2.3. Exploratory Objectives

The exploratory objectives of the study are:

- to evaluate the efficacy of VP-102 by assessing the proportion of subjects exhibiting reduction of ≥ 1 treatable wart from baseline at each scheduled post baseline visit.
- to evaluate the efficacy of VP-102 by assessing the proportion of subjects who are clear at the Study Day 84 EOT Visit and remain clear at the Follow-up Visits on Study Days 112 and 147 EOS.
- to evaluate the efficacy of VP-102 by assessing the change from baseline in total wart area (sum of individual warts) at the scheduled post baseline visits Day 84, 112, and 147.
- to evaluate the efficacy of VP-102 by assessing the percent change from baseline in total wart area (sum of individual warts) at the scheduled post baseline visits Day 84, 112, and 147.

3. Study Design

This is a phase 2, double-blind, placebo-controlled study to determine the dose regimen, safety, tolerability, and efficacy of VP-102 in subjects with EGW. The study population will consist of adult subjects (18 years of age or older) with a wart count of 2-30 and a duration greater than or equal to 4 weeks at baseline. The study is divided into two parts: Part A (dose regimen finding) and Part B (safety and efficacy). The study will consist of

a screening period (up to 14 days prior to first treatment), treatment period (4 visits), and a follow-up period.

In Part A, approximately six subjects will be enrolled into one of three groups for treatment skin exposure (for a total of 18 subjects): Group 1: 2-hour, Group 2: 6-hour, or Group 3: 24-hour. Each group will include a minimum of two subjects from each gender and will be randomized to VP-102 or placebo in a 5:1 ratio within each group. Study drug will be administered once every 21 days (+/- 4 days) for up to four applications. Enrollment will begin in Group 1 and then proceed to Group 2 and finally 3 after completion of a blinded review of the safety and tolerability data by a Safety Review Panel performed 48 hours post treatment during Treatment Period 1. After Group 3 subjects have completed, an additional blinded review will be conducted to determine the dose selections for Part B.

In Part B, approximately 90 subjects will be enrolled and randomized to one of four treatment arms: VP-102 Regimen 1, Placebo Regimen 1, VP-102 Regimen 2, or Placebo Regimen 2, in a 3:2:3:2 ratio, respectively and stratified by gender. Regimen 1 and 2 refer to one of the skin exposure times (2-hour, 6-hour, or 24-hour) selected from Part A. Procedures for Part B will follow those in Part A with the exception of the Safety Review Panel.

4. Determination of Sample Size

No formal power calculations were performed for this study. The study will enroll approximately 18 subjects in Part A to determine the dose selection and approximately 90 subjects in Part B to evaluate wart clearance rates and support future trials.

5. Statistical Methods

The statistical analyses will be reported using summary tables, figures and listings (TFLs). Numbering for TFLs will be based on the recommended numbering convention provided by the International Conference on Harmonization. Continuous variables will be summarized with means, standard deviations, medians, minimums and maximums. Categorical variables will be summarized by counts and percent of subjects in corresponding categories. Where appropriate, 95% confidence intervals will be included. Missing values are not considered for percent calculations, unless stated otherwise. In those cases, footnotes will specify the percent basis.

Individual subject data obtained via the electronic data capture (EDC) system and from external vendors will be presented in listings and sorted by subject number and visit/visit date if appropriate. Data will be summarized in tables and/or figures by treatment group.

Treatments in Part A will be pooled with Part B where applicable. For example, if VP-102 24-hour exposure is one of the treatments selected for Part B, then the data from Group 3 (24-hour exposure) in Part A will be pooled with the 24-hour exposure data in Part B. The data from Part A will be summarized separately in a descriptive manner. Treatment comparisons will be made separately for each regimen, i.e., VP-102 Regimen 1 vs Placebo Regimen 1 and VP-102 Regimen 2 vs Placebo Regimen 2.

The analyses described in this plan are considered *a priori*, in that they have been defined prior to database lock. Any analysis added after the database lock will be considered *post hoc* and exploratory. *Post hoc* analyses will be labeled as such on the output and identified in the CSR. All analyses and tabulations will be performed using SAS® version 9.3 or higher. Tables and listings will be presented in .rtf or .pdf format. Upon completion, all SAS programs for tables will be validated by an independent programmer. The validation process will be used to confirm that statistically valid methods have been implemented and that all data manipulations and calculations are accurate. Checks will be made to ensure accuracy, consistency with this plan, consistency with tables and consistency between tables and corresponding data listings.

6. Analysis Populations

The Intent-to-Treat population (ITT) will include all randomized subjects.

The Per-Protocol (PP) population will include subjects who receive all planned treatments of study drug (i.e., complete up to four treatments within the Day 75 treatment window or achieved complete clearance prior to Day 75), had no major protocol violations, and were assessed for clearance at Study Day 84 (up to 92 days) EOT Visit.

The Safety population will include all randomized subjects who receive at least one application of study drug.

7. Study Population

7.1. Subject Disposition

The number of subjects randomized and number of subjects in each population will be summarized by treatment group. Also included will be the number of subjects who completed through Day 84, number of subjects assessed for clearance at Day 84 based on analysis windows, number of subjects with major protocol violations, number of subjects who received all planned treatments of study drug by Day 75 or achieved complete clearance prior to Day 75, number of subjects completing and discontinuing the study, along with the primary reason for discontinuation. The completion/discontinuation status refers to the subject's participation in the study; therefore, the data is collected at the last

scheduled visit, Study Day 147 EOS. If a subject discontinues the study prematurely, then the case report form is completed at the time of discontinuation.

7.2. Protocol Deviations

Protocol deviations will be collected throughout the study. Deviation type, as reported in the EDC, will be summarized by treatment group for those deviations classified as major.

7.3. Demographic and Baseline Characteristics

Demographic variables will include age, sex, ethnicity and race. Age will be calculated using the date of informed consent.

Baseline characteristics will include wart history, Fitzpatrick Skin Type, height, weight and body mass index (BMI). BMI will be calculated as weight (kg) / height (m²). Wart history variables that will be summarized include time since clinical diagnosis in years (as compared to informed consent), age at diagnosis in years (derived using birth date year), number of months warts have been present (derived using informed consent date and clinical diagnosis date) and any previous treatments for warts. If the clinical diagnosis date is not complete, the date will be imputed as follows: (a) if the day is missing then it will be set to the first day of the month; (b) if the month is missing then it will be set to January; (c) if the year is missing then the date will be set to missing and will therefore not be included in the summary of time since clinical diagnosis.

The baseline efficacy data will be summarized by treatment group also. Specifically, the number of warts, anatomical location by gender, and wart area diameter will be presented.

Demographics and baseline characteristics will be summarized by treatment group for all 3 analysis populations (ITT, PP, Safety).

8. Efficacy Analysis

The primary analysis population will be the ITT population. However, the PP population will also be used for efficacy analysis. Results will be summarized by the treatment group to which each subject was randomized. Where appropriate, 95% confidence intervals and p-values may be generated as well. Efficacy parameters will be summarized for both Part B pooled with Part A for the applicable treatments and separately for the treatment not selected from Part A. Treatment comparisons will be made separately for each regimen, i.e., VP-102 Regimen 1 vs Placebo Regimen 1 and VP-102 Regimen 2 vs Placebo Regimen 2. A sensitivity analysis in which each of the VP-102 Regimens will be compared individually to the pooled Placebo Regimens on the primary endpoint will be conducted on the ITT population. Additionally, the VP-102 Regimens will be pooled

and compared to the pooled Placebo Regimens for the primary endpoint on the ITT population.

On the Wart Count case report form (CRF), the total number of overall EGW warts is collected. Genital warts that develop in areas that are unable to be treated or other types of warts will not be evaluated, documented, or considered in the analysis.

Some efficacy endpoints will be summarized by treatment visit. Treatments are planned to occur every 21 (+/- 4) days as long as warts are present for up to 4 treatments within the 75 day treatment period. Treatment may be delayed for various reasons, including but not limited to ongoing LSRs. As a result, the timing of when subjects receive treatment may vary. For the purpose of summarizing treatment visits, only visits when treatment was given will be considered. Moreover, a window will be applied to each visit to ensure that subjects are compared at the same treatment durations. A window of +/- 10 days from the targeted treatment schedule will be used. The table below summarizes the windows. These windows will be used on all by-visit summaries.

Visit	Target Day	Window
1	1	N/A
2	21	11 – 31
3	42	32 – 52
4	63	53 – 73
Day 84 EOT	84	74 – 94
Follow-up Day 112	112	95 – 129
Follow-up Day 147	147	130 – 157

If more than one visit falls within a window, then the visit closest to the target day will be used in the analysis. Visits when treatment was planned but treatment was not applied will be recorded as “Unscheduled”. Unscheduled visit information will not be considered for by-treatment visit summary tables. However, all efficacy data will be presented in data listings.

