ERT assessments, wart count, and wart location will be conducted before treatment application at all Treatment Visits 1 to 4, as well as at the EOT Visit on Study Day 84 (0/+8 days) and at the Follow-up Visits on Study Day 112 (± 7 days) and Study Day 147 (± 7 days). Wart measurement will be conducted before treatment application at Treatment Visit 1, as well as at the EOT Visit on Study Day 84 (-0/+8 days) and at the Follow-up Visits on Study Day 112 (± 7 days) and Study Day 147 (± 7 days). Subjects who clear all warts before the Study Day 84 (EOT) Visit will still be required to return for each of the scheduled in-person treatment visits, as well as the Study Day 84 (EOT) Visit, the Study Day 112 follow-up visit, and the Study Day 147 (EOS) Visit. A Provider Treatment Questionnaire will be completed at the Study Day 84 (EOT) Visit by a clinician who applied treatment to the subject during the course of the study. All subjects will continue in the study for two additional Follow-up Visits on Study Day 112 and Study Day 147 (EOS).

All treatment visits will include a wart count, performed before treatment (if applicable) and before ERT assessment. No treatment will be required if the wart is considered clear. Genital warts that develop in areas that are unable to be treated, (e.g., close to a

mucous membrane) and other wart types (e.g., common warts) will not be evaluated, documented, or considered in the analysis.

Wart counts will be conducted at the Screening Visit, Treatment Visit 1, Treatment Visit 2, Treatment Visit 3, Treatment Visit 4, End of Treatment Visit, and Follow-up Visit by a trained member of the study team. Other than the screening visit and Day 1, wart counts will also be conducted by a member of the research team that has been identified and trained as a Blinded Assessor. The Blinded Assessor may be utilized for a subject's initial screening, enrollment and treatment Visit 1 activities, however, may not perform any other study related activities other than wart counts at subsequent visits (e.g., follow-up phone calls or unscheduled visits) for the same subject. The Blinded Assessor is not required to be the same person for each assessment.

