8.1. Efficacy Variables

Primary endpoint:

- Proportion of subjects exhibiting complete clearance of all treatable warts (baseline and new) at the Study Day 84 EOT Visit.

Secondary endpoints:

- Proportion of subjects exhibiting complete clearance of all treatable warts (baseline and new) at Visit 2, Visit 3, Visit 4, Follow-up Day 112, and Follow-up Day 147 EOS.

- Proportion of subjects exhibiting 90% and 75% clearance of all treatable warts (baseline and new) at Visit 2, Visit 3, Visit 4, Study Day 84 EOT, Follow-up Day 112, and Follow-up Day 147 EOS.
- Change from baseline in the number of treatable warts (baseline and new) at Visit 2, Visit 3, Visit 4, Study Day 84 EOT, Follow-up Day 112, and Follow-up Day 147 EOS.
- Change from baseline in the percent of treatable warts (baseline and new) at Visit 2, Visit 3, Visit 4, Study Day 84 EOT, Follow-up Day 112, and Follow-up Day 147 EOS.

Exploratory endpoints:

- Proportion of subjects exhibiting reduction of at least 1 treatable wart from baseline at Visit 2, Visit 3, Visit 4, Study Day 84 EOT, Follow-up Day 112, and Follow-up Day 147 EOS.
- Proportion of subjects who are clear at the Study Day 84 EOT Visit and remain clear at the Follow-up Day 112 and 147 EOS Visits.
- Change from baseline in total wart area (sum of individual warts) at Study Day 84 EOT, Follow-up Day 112 and Follow-up Day 147 EOS.
- Change from baseline in the percent of total wart area (sum of individual warts) at Study Day 84 EOT, Follow-up Day 112, and Follow-up Day 147 EOS.

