8.4. Handling of Dropouts or Missing Data

All subjects who were randomized will be evaluated in the ITT population. If a subject requests to be removed from the study due to study related adverse events or additional spreading of disease, data will be collected and analyzed as a treatment failure and not replaced. If a subject discontinues use of study drug but remains in the study, the subject will be analyzed as a non-responder as well. Per the study protocol, subjects who achieve complete clearance of all lesions prior to Day 84 are required to attend all Treatment Visits but will not receive treatment at those visits where all lesions are clear. These subjects will not be considered as having prematurely discontinued use of the study drug.

Unless described otherwise in subsequent sections, analyses will be carried out with the data available using no imputation for missing data. A description of how missing data will be handled for select endpoints is included below.

8.4.1. Coronavirus 19

Due to the coronavirus 19 (COVID-19) outbreak during the course of the study, there may be several subjects who will have missing assessments which could affect the primary analysis. Subjects who are unable to attend a study visit due to COVID-19 will be documented in the protocol deviation log. The protocol deviation date will be used as the COVID-19 affected date (or visit). If a subject reports an adverse event of COVID-19, then the event start date will be used as the affected date. In the event that a subject has an affected COVID-19 date from both sources, the earlier of the dates will be used.

Subjects who were affected by COVID-19 will be summarized in a data listing. The listing will contain the following information: subject number, treatment, gender, age, first date affected by COVID-19, duration in study prior to the affected COVID-19 date, total study duration, exposure to study drug, any COVID-19 related adverse events, completion/discontinuation of the study, and reasons for discontinuation. All data listings will include a flag to denote whether the subject and/or visit was affected by COVID-19.

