8.4.2. Handling of Missing Data for Complete Clearance Endpoint

The efficacy endpoint, proportion of subjects exhibiting complete clearance of all treatable warts, is to be assessed (blinded assessment only) at Treatment Visits 2, 3, 4, Study Day 84 EOT visit, and Follow-up visits Day 112 and 147.

For the primary efficacy analysis, subjects who do not have an assessment of complete clearance of all treatable warts at any of the scheduled assessments (with applicable visit windows applied) will be considered to have not achieved complete clearance of all treatable warts at that visit.

Due to COVID-19, sensitivity analyses will be performed to assess the robustness of the primary analysis. The purpose of these analyses is to assess any potential bias due to subject assessments or missing data due to COVID-19. There will be two sensitivity analyses on the primary efficacy endpoint, complete clearance at Day 84.

- Exclude COVID-19 affected data: The first analysis will be to conduct the planned analysis only on the subjects who were not affected by COVID-19 at or before Day 84 (with visit window), i.e., if a subject was affected by COVID-19, then the subject will be removed from the analysis.
- Multiple imputation of missing data: The second analysis will be to use the multiple imputation regression method. For monotone missing data patterns, data in each treatment group will be imputed using the regression method on the basis of the predicted future pattern for the same treatment group. One hundred imputed

datasets will be generated. Each imputed dataset is analyzed separately using the method for the efficacy endpoint described in 9.1. The final estimate of treatment difference will be the average of the estimates based on the 100 individual imputed datasets. The pooling of the individual estimates and inferences based on the combined estimate will be handled by the SAS procedure MIANALYZE.

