9.1. Complete Clearance of Treatable Warts

Counts and percent of subjects who have complete clearance of all treatable warts will be displayed by visit; however, the primary analysis is complete clearance at Study Day 84 EOT. The row mean scores statistic from the Cochran-Mantel-Haenszel (CMH) test will be used to analyze differences in each treatment regimen (VP-102 Regimen 1 vs Placebo Regimen 1 and VP-102 Regimen 2 vs Placebo Regimen 2) by gender. Complete clearance will be defined as no warts (treatable wart count=0) reported for a subject per the blinded EGW Wart Count form. This analysis will be done on the primary endpoint, Study Day 84, as well as each of the other visits.

Also analyzed will be the proportion of subjects who have complete clearance at Day 84 and remained clear through the end of the study, follow-up visit Day 147. The CMH test will be used to test for treatment differences.

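### Taken literally, the SAP's treated-visits-only rule discards the zero counts of subjects who are clear and untreated at Visits 2-4, so the secondary clearance rates there would come out near 0%

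*SAP*

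**What the plan says.** SAP Section 8 opens its visit-window text with "Some efficacy endpoints will be summarized by treatment visit" and does not name those endpoints. It notes that treatment can be delayed, for instance by local skin reactions (LSRs), and sets the rule: "For the purpose of summarizing treatment visits, only visits when treatment was given will be considered". A second rule follows: "Visits when treatment was planned but treatment was not applied will be recorded as" Unscheduled, and Unscheduled visits are left out of the by-treatment-visit tables.

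SAP 8.4 says that subjects who clear early "are required to attend all Treatment Visits but will not receive treatment at those visits where all lesions are clear". Protocol 6.1.3.2 agrees: "No treatment will be required if the wart is considered clear".

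SAP 8.1 lists as a secondary endpoint: "Proportion of subjects exhibiting complete clearance of all treatable warts (baseline and new) at Visit 2, Visit 3, Visit 4, Follow-up Day 112", and Day 147. SAP 9.1 defines clearance as a treatable wart count of zero on the blinded form and adds: "This analysis will be done on the primary endpoint, Study Day 84, as well as each of the other visits". For subjects without an assessment, SAP 8.4.2 reads in part: "with applicable visit windows applied) will be considered to have not achieved complete clearance of all treatable warts at that visit". SAP 8.4.3 applies no imputation to the wart-count endpoints.

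**The concern.** Being clear leads to no treatment; no treatment removes the visit from the summary; and a missing assessment is scored as failure. The planned Visit 2-4 clearance analysis is thus emptied by the visit-selection rule of the same plan. A programmer who followed Section 8 to the letter would report clearance close to zero in every arm, whatever happened to the warts. The results for 75% and 90% clearance, loss of at least one wart, and change and percent change in count at Visits 2-4 would lose the same zeros. The loss is greatest in the arm that clears most subjects early, so the treatment contrast shrinks too.

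This matters because the study's stated use is to inform wart clearance rates for later placebo-controlled trials (Protocol 12.6, SAP Section 4).

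**Working it through.** The plan states no clearance rate, effect size or power, so there is no figure of its own to reproduce.

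**Inputs from the documents**
- Part B: 90 subjects at 3:3:2:2, so 90 × 3/10 = 27 per VP-102 arm and 90 × 2/10 = 18 per placebo arm.
- Part A: 6 per group at 5:1 adds 5 and 1 to each selected regimen. Pooled comparison: 27 + 5 = 32 versus 18 + 1 = 19.
- A blinded-clear subject can still be treated in two ways: the clinician is unsure whether a wart remains (Protocol 6.1.3.2), or the separate study-team count differs from the blinded count (Protocol 9.3.2.1). No frequency is given.

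**Assumed ranges**
- p, the true blinded clearance rate at a visit: 10-30%.
- q, the share of blinded-clear subjects treated anyway: 0-30%.

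**Complete clearance**
- Dropped visit scored as not clear (SAP 8.4.2): reported = p × q.
- Dropped visit leaves the denominator (the SAP Section 5 default): reported = pq / (1 − p(1 − q)).

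| True p | q | Scored not clear | Leaves denominator |
|---|---|---|---|
| 10% | 0 | 0% | 0% |
| 10% | 30% | 3.0% | 3.2% |
| 20% | 30% | 6.0% | 7.0% |
| 30% | 0 | 0% | 0% |
| 30% | 5% | 1.5% | 2.1% |
| 30% | 20% | 6.0% | 7.9% |
| 30% | 30% | 9.0% | 11.4% |

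At p = 30%, 0.30 × 32 = 9.6 VP-102 subjects are clear. Between 0 and 0.30 × 9.6 = 2.9 of them would be counted.

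**Chance that the exploratory comparison gives p < 0.05** (exact enumeration of the unstratified CMH statistic, 32 versus 19)

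| True rates | Zeros kept | q = 0 | q = 20% | q = 30% |
|---|---|---|---|---|
| 30% vs 5% | 65.0% | 0% | 0.9% | 4.8% |
| 20% vs 5% | 31.1% | 0% | 0.2% | 0.9% |
| 10% vs 5% | 4.1% | 0% | 0.1% | 0.1% |

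**Other wart-count endpoints at Visits 2-4** (observed cases)
- At least 75% clearance, with true rate r: reported = (r − p(1 − q)) / (1 − p(1 − q)). For r = 50% and p = 30%: 0.20/0.70 = 28.6% at q = 0, and 0.29/0.79 = 36.7% at q = 30%.
- Mean percent change, assuming 30% clear and −50% in the rest: true = 0.3 × (−100) + 0.7 × (−50) = −65%; reported at q = 0 is −50%.

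**Simulation for the model-based results.** It used 54 settings of 4,000 subjects per arm, with no dropout and no new warts. Assumed inputs were mean baseline counts of about 5, 8 or 12 limited to 2-30; per-wart clearance per cycle of 15, 25 or 40% on VP-102 and 4% on placebo; three degrees of between-subject spread; and q of 0 or 30%. The repeated-measures model had the SAP 9.2 terms and an unstructured covariance, but was fitted by maximum likelihood, not by REML with Kenward-Roger. Understatement at Visit 4 on VP-102, in percentage points:

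| Result | 42 settings with true clearance 5-35% | All 54 settings |
|---|---|---|
| At least 75% clearance | 3.4-25.8 | 1.6-32.7 |
| Raw mean percent change | 2.3-18.7 | 1.1-24.1 |
| MMRM percent change | 0.4-4.2 | 0.3-6.8 |

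The Day 84 MMRM difference from placebo moved by at most 0.04 point.

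**The case against.** The strongest reply is that the rule was never meant for clearance. Section 8 ties it to only some endpoints and explains it by delayed treatment. SAP 9.1 displays clearance by visit, not by treatment visit. SAP 8.4.2 scores as failures only those without an assessment, and a clear subject who attended has one. The Unscheduled label does not obviously catch clear visits either, since Protocol 9.6 links untreated visits under that label to ongoing LSRs. As a statement of intent this is persuasive. It does not settle the text: SAP 8.4.2 itself places the clearance assessment at Treatment Visits 2, 3 and 4, Section 8 selects treatment visits by whether drug was given, and no exception is written. The SAP 8.4 sentence that protects clear subjects concerns only whether they count as having discontinued study drug.

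Three further points have some force.
- **Denominator.** SAP 8.4.2 overrides the Section 5 default for clearance, so p × q is the better-supported figure.
- **Assumptions.** The 65% belongs to one favourable pair of rates. The enumeration ignores the planned gender stratification, and the simulation inputs have no source in the documents. For the planned MMRM the bias is modest.
- **Selection by outcome.** Keeping untreated clear visits while dropping untreated visits with warts could tilt observed-case results towards response. This is largely answered: the Unscheduled procedures in Protocol 9.6 and Table 1 list no wart count, so few blinded counts would be lost there.

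Independent validation (SAP Section 5) might catch zero rates that clash with the listings, but it also checks consistency with the plan, and here the plan is the source of the error.

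**Conclusion.** The concern holds as a literal reading, and it should be fixed. As written, SAP Section 8 reduces complete clearance at Visits 2, 3 and 4 from p to p × q: zero if no blinded-clear subject is treated, and at most 9% for a true 30% when 30% of such subjects are treated. The direction follows from the rule; the size rests on assumed p and q. The wart-count endpoints at the same visits are also understated, substantially in the raw summaries and much less in the MMRM.

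The limits are clear. The primary Day 84 clearance analysis and the Day 112 and 147 clearance rates are untouched, listings retain all efficacy data, and SAP 8.6 makes every comparison exploratory. The likely cause is a drafting slip aimed at delayed treatments.

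**What to change.** Keep the treated-only and Unscheduled rules for visits where warts were present but treatment was delayed. Add to the visit-window text of SAP Section 8:

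> A scheduled treatment visit at which no treatment was applied because the subject was clear is not Unscheduled; it is included in all by-visit efficacy summaries for its window, using the blinded wart count recorded at that visit.

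The cost is one sentence of SAP wording before database lock. No new data are needed, since Protocol 9.3.2.1 already has a Blinded Assessor count warts at Treatment Visits 2-4, and no study procedure changes.
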